5.8 Specimen Submission for Correlative and Pharmacogenomic Substudies

All participating institutions must ask patients for their consent to participate in the components of the correlative (CALGB 150911) and pharmacogenomic (CALGB 60905) substudies planned for CALGB/SWOG C80702, although patient participation is optional. Rationale and methods for the scientific components of these studies are described in Appendices II and III.

Type of specimen	Pre-treatment
Tissue*	2 paraffin blocks (1 tumor / 1 normal)
EDTA Plasma (lavender top)*	1 x 10 mL
Serum (red top)*	1 x 10 mL
Whole Blood (lavender top)**	1 x 10 mL
[Total blood volume]	[30 mL]

* For patients who answer “yes” to consent question #2 (CALGB 150911).

** For patients who answer “yes” to consent question #3 (CALGB 60905). Note: Specimen is requested to be drawn pre-treatment but can be drawn at any time while the patient is on study.

USE OF THE ALLIANCE BIOSPECIMEN MANAGEMENT SYSTEM (BioMS) IS MANDATORY AND ALL SPECIMENS MUST BE LOGGED AND SHIPPED VIA THIS SYSTEM.

BioMS is a web-based system for logging and tracking all biospecimens collected on Alliance trials. Authorized individuals may access BioMS at the following URL: [redacted] using most standard web browsers (Safari, Firefox, Internet Explorer). For information on using the BioMS system, please refer to the ‘Help’ links on the BioMS web page to access the on-line user manual, FAQs, and training videos. To report technical problems, such as login issues or application errors, please contact: [redacted] For assistance in using the application or questions or problems related to specific specimen logging, please contact: [redacted]

After logging collected specimens in BioMS, the system will create a shipping manifest. This shipping manifest must be printed and placed in the shipment container with the specimens.

All submitted specimens must be labeled with the protocol number (C80702), patient study ID number, patient’s initials and date and type of specimen collected (e.g., serum, whole blood).

A copy of the Shipment Packing Slip produced by BioMS must be printed and placed in the shipment with the specimens.

Instructions for the collection of samples are included below. Please be sure to use a method of shipping that is secure and traceable. Extreme heat precautions should be taken when necessary.

Shipment on Monday through Thursday by overnight service to assure receipt is encouraged. Do not ship specimens on Fridays or Saturdays.

5.8.1 Submission of Paraffin Blocks of Archived Colorectal Tissue (CALGB 150911)

For patients who consent to Question #2, tissue blocks will be used for the correlative studies described in [Appendix II](#). Paraffin blocks of tissue obtained from archival colorectal specimens from primary site should be sent to the Alliance Biorepository at Ohio State University (OSU). Submit 1 block of tumor tissue and 1 block of normal tissue.

The Alliance has instituted special considerations for the small percentage of institutions whose policies prohibit release of any blocks. If, due to institutional policy, a block cannot be sent, please call [REDACTED] to obtain a protocol for submission of representative tissue from your institution.

The goal of the Alliance Biorepository at Ohio State University (OSU) is to provide investigators with quality histology sections for their research while maintaining the integrity of the tissue. All paraffin blocks that are to be stored at the OSU will be vacuum packed to prevent oxidation and will be stored at 4°C to minimize degradation of cellular antigens. For these reasons it is preferred that the OSU bank the block until the study investigator requests thin sections. Please contact the OSU if additional assurances with your hospital pathology department are required.

5.8.2 Plasma Collection Procedures (CALGB 150911)

For patients who consent to consent question #2, plasma samples will be used for the studies described in [Appendix II](#).

1. Collect blood in 10 mL lavender top tube. After collection, gently mix the blood by inverting the tube 8 to 10 times. Store vacutainer tubes upright at 4°C until centrifugation. Blood samples should be centrifuged within four hours of blood collection.
2. Centrifuge blood samples in a horizontal rotor (swing-out head) for 10 to 15 minutes at 1100-1300 g at room temperature. Warning: Excessive centrifuge speed (over 2000 g) may cause tube breakage and exposure to blood and possible injury. If needed, relative centrifugal force (RCF) for a centrifuge can be calculated. For an on-line calculator tool, please refer to: [REDACTED]
3. After centrifugation, plasma layer will be at the top of the tube. Mononuclear cells and platelets will be in a whitish layer, called the “buffy coat”, just under the plasma and above the red blood cells.
4. Carefully collect the plasma layer with an appropriate transfer pipette without disturbing the buffy coat layer. Pipette the plasma into the labeled cryovials (recommended cryovials are described in [Section 5.8.4](#)). Aliquot volume is to be 500 µL. Close the caps tightly and place on ice. This process should be completed within 1 hour of centrifugation.
5. Check that all aliquot vial caps are secure and that all vials are labeled.
6. Place all aliquots upright in a specimen box or rack in an -80°C or colder freezer. All specimens should remain at -80°C or colder prior to shipping. The samples should not be thawed prior to shipping. Plasma should be shipped on dry ice according to the shipping procedures in [Section 5.8.4](#).

5.8.3 Serum Collection Procedures (CALGB 150911)

For patients who consent to consent question #2, serum samples will be used for the studies described in [Appendix II](#).

1. Collect blood in 10 mL red top tube. After collection, tubes (“vacutainers”) should sit upright after the blood is drawn at room temperature for a minimum of 30 to a maximum of 60 minutes to allow the clot to form. Note: Use red top (serum) tubes (silicon-coated)—no additives and not SST (serum separator tubes).
2. Centrifuge the blood sample at the end of the clotting time (30-60 minutes) in a horizontal rotor (swing-out head) for 10-15 minutes at 1100-1300 g at room temperature.
3. Use a pipette to transfer the serum (Recommendation: do not pour). Pipette serum into the labeled cryovials (recommended cryovials are described in [Section 5.8.4](#)). Aliquot volume is to be 500 μ L. Close the cap on the vial tightly. This process should be completed within 1 hour of centrifugation. Note: Be very careful not to pick up red blood cells when aliquoting. This can be done by keeping the pipet above the red blood cell layer and leaving a small amount of serum in the tube.
4. Check that all aliquot vial caps are secure and that all vials are labeled.
5. Place all aliquots upright in a specimen box or rack in an -80°C or colder freezer. All specimens should remain at -80°C or colder prior to shipping. The samples should not be thawed prior to shipping. Serum should be shipped on dry ice according to the shipping procedures in [Section 5.8.4](#).

5.8.4 Plasma and Serum Processing Procedures

The Alliance strongly recommends the usage of 2 mL cryovials for storage of plasma and serum specimens. Acceptable cryovials include:

Company name	Catalog number
Nalgene	03-337-7Y (through Fisher) NNI No.: 5012-0020
Fisher brand	05-669-57 (through Fisher)
Corning	03-374-21 (through Fisher) CLS430659 (through Sigma) Corning: 430488
VWR	16001-102

All samples should be labeled with the patient’s initials, CALGB treatment study number (CALGB/SWOG C80702), patient study ID number, date and time of collection, and sample type. The sample should be shipped on dry ice to the Alliance Biorepository at Ohio State University (OSU).

5.8.5 Whole Blood Submission for the Pharmacogenomic Substudy (CALGB 60905)

For patients who consent to question #3, whole blood will be used for the pharmacogenomic studies described in [Appendix III](#). This sample should be collected prior to the initiation of protocol treatment. Note: Specimen is requested to be drawn pre-treatment but can be drawn at any time while the patient is on study.

Draw 10 mL of venous blood in a lavender top (EDTA coagulant) tube and keep refrigerated until shipped overnight to the Alliance Biorepository at Ohio State University (OSU). Label the tube with the patient’s initials, patient study ID number, CALGB treatment number (CALGB/SWOG C80702) and date of collection. The sample should be shipped the same

day on a cold pack by overnight mail to the Alliance Biorepository at Ohio State University (OSU).

5.9 Data Submission for Cancer Prevention Companion Studies (CALGB 71002)

At registration, patients may elect to enroll on the cancer prevention studies ([Appendices IV and V](#)) by consenting to question #1. These studies will require patients to complete a Diet and Lifestyle survey and agree to the submission of their colonoscopy and pathology reports as described below.

Diet and Lifestyle Survey:

Surveys will be sent by [REDACTED] (see below) to individual treatment centers within 2 weeks of registration. Versions of the surveys are available in Spanish and French – please email [REDACTED] requesting these versions if required for the patient. Patients should complete the first survey within 6 weeks of randomization. Patients should also complete questionnaires 14-16 months from randomization. It is recommended that the surveys be completed during a physician visit, likely during the infusion of chemotherapy. Questions regarding the survey should be directed to [REDACTED]. Completed surveys should be mailed by the institutional CRA to the following address:

[REDACTED]
 [REDACTED]
 [REDACTED]
 [REDACTED]
 [REDACTED]
 [REDACTED]

Colonoscopy and Pathology Reports:

According to NCCN and US Multi-Society Task Force guidelines, it is recommended that patients have a colonoscopy performed within 12 months of diagnosis. Clinical considerations should dictate the exact timing (i.e., if the patient’s initial colonoscopy at diagnosis was not a complete exam or the patient did not have a colonoscopy at diagnosis, guidelines suggest the first post-treatment colonoscopy be performed sooner than 12 months after surgery – typically after completion of adjuvant FOLFOX). A second post-treatment colonoscopy should be performed within 3 years of the first post-treatment colonoscopy, but may be performed earlier based on findings from the first colonoscopy as well as other clinical conditions. Earlier timing should be dictated by the clinical judgment of the gastroenterologist, oncologist and/or surgeon.

All colonoscopy reports obtained within the first 6 years after randomization should be submitted via Medidata Rave®. If any biopsies were taken during those colonoscopies, those pathology reports should also be submitted via Medidata Rave®. See [Section 5.7](#) for data submission instructions.

6.0 REQUIRED DATA

Pre-Study Testing Intervals

To be completed within 16 DAYS before registration:

- All bloodwork, history and physical, and pregnancy test.

To be completed within 80 DAYS before registration (preoperative scans acceptable):

- CT or MRI abdomen/pelvis or PET-CT scan without evidence of metastatic disease
- CT chest or chest X-ray (PET-CT including chest, is acceptable) without evidence of metastatic disease

	Prior to Registration*	Day 1 of each tx w/ FOLFOX*	During tx w/ Celecoxib Placebo only**	Post-tx Follow Up***
Tests & Observations				
History and Physical Examination	X	A	X	X
Pulse, Blood Pressure	X	A	X	X
Height	X			
Weight/Body Surface Area ϕ	X	X	X	X
Performance Status	X	A	X	X
Drug Toxicity Assessment		X	X	X
Celecoxib/Placebo Adherence#		B	B	
Laboratory Studies				
CBC, Differential, Platelets	X	X		
Serum Creatinine and BUN	X	C	F	
AST, Alk Phos., Total Bilirubin	X	C	F	
PT/INR	D	D	D	
Pregnancy Test (UCG) ‡	X			
CEA	X		E	E
STAGING				
Chest x-ray (PA & Lateral) or Chest CT	X		E	E
Abdominal/pelvic Imaging: (CT, MRI or PET-CT scan)	X		E	E
Companion Studies Ψ				
Diet & Lifestyle / Other Meds / Comorbidities Questionnaire	To be completed w/in first 6 weeks of randomization and 14-16 months after randomization. See Section 5.9.			
Colonoscopy and Pathology Reports	See Section 5.9.			
Tumor Block	To be collected pre-treatment (see Section 5.8).			
Whole Blood, Plasma, and Serum	To be collected pre-treatment (see Section 5.8).			

* Pre-registration H&P, vital signs, labs and clinical assessments may be used for Day 1 of Cycle 1. For subsequent cycles, H&P and labs may be obtained within 72 hours prior to day of treatment (96 hours if due to holidays).

** Every 3 months until 3 years after initiation of celecoxib/placebo or until disease progression, whichever comes first.

*** Every 6 months until 6 years after randomization or until disease progression, whichever comes first. Once a patient has progressive disease, submission of follow-up forms is still required for survival data. See forms schedule in [Section 5.7](#).

A While on FOLFOX, patients should have a physical exam and report capsule counts of celecoxib/placebo prior to cycles 3 and 5 for study arms C and D and prior to cycles 3, 5, 7, 9 and 11 for study arms A and B. If treatment is held due to toxicity, physical exam and capsule count does not need to be repeated on the day that therapy is resumed.

B Patients will record daily intake of study medication on diary starting when the patient begins taking celecoxib/placebo (no later than cycle 2 day 1 of FOLFOX).

C Prior to cycles 3 and 5 for study arms C and D and prior to cycles 3, 5, 7, 9 and 11 for study arms A and B.

D Only for those patients receiving coumadin/warfarin: PT/INR should be monitored weekly during FOLFOX. During celecoxib monotherapy, PT/INR should be monitored at least every other week for the first month, then as clinically indicated.

E For patients who were randomized to 6 treatments of FOLFOX, the first post-treatment CEA and imaging should occur within 4 months after completion of FOLFOX. For patients who were randomized to 12 treatments of FOLFOX, the first post-treatment CEA and imaging should occur within 6 weeks of FOLFOX (see [Section 11.0](#)). Then, for all patients, every 6 months from last scan until at least 3 years after initiation of celecoxib/placebo and then yearly for 3 years, or until disease progression. CEA and scans may be performed +/- 1 month of next testing due date.

F May be obtained 28 days in advance of follow-up appointment

Pill counts should include collection and review of monthly diaries as outlined in [Section 7.3](#).

ϕ It is not necessary to change the doses of chemotherapy unless the calculated dose changes by $\geq 10\%$.

‡ For women of child-bearing potential.

Ψ For those patients who consent to participate in the substudies.

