7.0 TREATMENT PLAN

Initiation of treatment must begin within 14 days after randomization. While not strictly an eligibility criterion, it is strongly recommended that patients begin treatment between 21 - 56 days after surgery. For patients who fall outside of this range or for any treatment-related questions, contact the Alliance or SWOG Study Chair.

This is a randomized, double-blind trial. No blinded starter supplies will be available for this study. Initial blinded, patient-specific clinical supplies of celecoxib / placebo will be shipped from the Pharmaceutical Management Branch (PMB) to the registering investigator at the time of patient randomization and should arrive within 7 to 10 days of randomization (see [Section 9.4](#)).

One cycle will be defined as 14 days of treatment. Cytotoxic chemotherapy will consist of 6 or 12 cycles of FOLFOX and daily celecoxib/placebo. Celecoxib/placebo will start by Day 1 of cycle 2 of FOLFOX.

7.1 FOLFOX, every 2 weeks.

- **Oxaliplatin** 85 mg/m² IV over two hours, **followed by**
- **Leucovorin** 400 mg/m² IV over two hours. Alternatively, leucovorin may be administered (via separate infusion containers) concurrently with oxaliplatin, **followed by**
- **5-FU** 400 mg/m² IV bolus, then 2400 mg/m² continuous IV infusion over 46-48 hours.

Patients receiving oxaliplatin on this study should be counseled to avoid cold drinks, chewing of ice chips, and exposure to cold water or air because the neurotoxicity often seen with oxaliplatin appears to be exacerbated by exposure to cold. The period of time during which the patient is at risk for these cold-induced sensory neuropathies is not well documented. Patients should exercise caution regarding cold exposure during the treatment period. Peripheral sensory neuropathies can occur at any time after receiving oxaliplatin therapy.

Continuous infusion 5-FU should be administered as specified, though early pump shut-offs do not need to be reported on forms unless >10% of dose was not administered.

In the event of a leucovorin shortage, refer to the CALGB 80702 study page, which can be found on the Alliance and CTSU websites.

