11.0 CRITERIA FOR RESPONSE, PROGRESSION, AND RELAPSE

To minimize potential bias of differential post-treatment surveillance between the two arms, CEA testing and imaging requires standardization. For patients who have signs or symptoms in which imaging is clinically indicated, the decision of timing of radiographic studies remains at the discretion of the treating clinician. However, for asymptomatic surveillance after the completion of FOLFOX, the timing of CEA testing and radiograph imaging must be similar. As such, for patients randomized to 6 treatments of FOLFOX, the first post-treatment CEA and imaging should occur approximately 4 months after completion of FOLFOX. For patients randomized to 12 treatments of FOLFOX, the first post-treatment CEA and imaging should occur within 6 weeks of completion of FOLFOX. CEA and scan may be performed +/- 1 month of next testing due date.

At the time of each evaluation, patients will be classified in the following manner:

No evidence of disease (NED)

OR

Recurrence of disease (REC): Recurrence must be confirmed by imaging and/or biopsy, with the colonoscopy and pathology reports submitted. Elevated CEA levels only or physical findings only will not be accepted as evidence of recurrence.

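### Do two wordings for the first scan after 6 FOLFOX treatments bias the 6- versus 12-treatment DFS comparison?

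*Combined protocol and SAP*

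**What the plan says.** Footnote E to the Section 6.0 test schedule states that, for patients randomized to 6 treatments, "the first post-treatment CEA and imaging should occur within 4 months after completion of FOLFOX". Section 11.0 states for the same patients that "the first post-treatment CEA and imaging should occur approximately 4 months after completion of FOLFOX". For the 12-treatment arm both places give an upper limit of 6 weeks after FOLFOX.

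Section 11.0 gives the reason for prescribing timing: "To minimize potential bias of differential post-treatment surveillance between the two arms, CEA testing and imaging requires standardization". It adds that for asymptomatic patients "the timing of CEA testing and radiograph imaging must be similar".

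Both passages allow the same tolerance: "CEA and scans may be performed +/- 1 month of next testing due date" in footnote E and "CEA and scan may be performed +/- 1 month of next testing due date" in Section 11.0. Footnote E cites Section 11.0, and it counts later scans at 6-month intervals from the previous one. Section 13.1 and Appendix VI, Section 1.1 date a DFS event by documentation of progression or recurrence, or by death.

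**The concern.** A limit with no lower bound is not the same rule as a target. A site following footnote E alone could scan a 6-treatment patient just after FOLFOX ends, while 12-treatment patients are still on chemotherapy. Because later scans are counted from the last one, an early first scan moves the following schedule too.

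Recurrences in the 6-treatment arm would then tend to be found, and so dated, earlier than in the 12-treatment arm. That would make 6 treatments look slightly worse in the DFS comparison that this trial contributes to the international non-inferiority pool (Section 2.2.1 and Appendix VI). It is the kind of bias that Section 11.0 sets out to prevent.

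**Working it through.** **1. The alignment Section 11.0 intends.** Section 7.0 gives the cycle length: "One cycle will be defined as 14 days of treatment". Take 1 month as 30.44 days, no treatment delays, and day 0 as the start of FOLFOX.

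- 6 treatments: 6 × 14 = day 84. Adding 4 × 30.44 = 121.75 gives about day 206 (week 29.4).
- 12 treatments: 12 × 14 = day 168. Adding 42 gives day 210 (week 30).

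The two points are about 4 days apart, so the Section 11.0 pair does what it sets out to do.

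**2. Windows under each reading (weeks from the start of FOLFOX).**

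| Reading | 6 treatments | 12 treatments |
|---|---|---|
| Footnote E, literal | 12 to 29.4 | 24 to 30 |
| Footnote E, literal, tolerance added at the upper end | 12 to 33.7 | 24 to 30 |
| Either passage, 4 months as due date, ± 1 month | 25.0 to 33.7 | 24 to 30 |

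The mismatch exists only in the first two rows.

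**3. Effect on the duration hazard ratio.** The simulation used 1,500,000 patients per arm and a true hazard ratio of 1. Onset followed the yearly failure probabilities in Section 13.1 (0.10, 0.12, 0.06, 0.05, 0.03, 0.02). Scans were 6-monthly to 3 years and then yearly, with detection at the next scan. Three inputs are assumptions that the documents do not supply: first scans uniform over the window, the share of recurrences found by symptoms at onset, and the share of events dated at onset as deaths. The spread of follow-up is also assumed. Entries are apparent hazard ratios, 6 versus 12 treatments.

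| Follow-up (years) | Symptoms / deaths | Footnote E literal | Footnote E to week 34 | Section 11.0 ± 1 month |
|---|---|---|---|---|
| 1.5 to 6 | 0% / 0% | 1.008 | 1.003 | 0.989 |
| 1.5 to 6 | 0% / 10% | 1.005 | 0.999 | 0.989 |
| 1.5 to 6 | 30% / 0% | 1.004 | 0.996 | 0.994 |
| 1.5 to 6 | 30% / 10% | 1.003 | 1.001 | 0.997 |
| 3 to 6.1 | 0% / 0% | 1.003 | 1.002 | 0.986 |
| 3 to 6.1 | 0% / 10% | 1.007 | 0.999 | 0.987 |
| 3 to 6.1 | 30% / 0% | 1.001 | 0.996 | 0.988 |
| 3 to 6.1 | 30% / 10% | 1.007 | 1.000 | 0.999 |

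The simulation error on the log hazard ratio is about 0.002, so values of 1.001 to 1.003 cannot be told from 1. In seven of the eight rows the Section 11.0 shift is as large as the literal footnote E shift or larger, in the opposite direction. The reason is that the 12-treatment limit is itself open below, so those scans can fall earlier than the 4-month target in the other arm.

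**4. Size against precision.**

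- This trial at 775 events: SE of the log hazard ratio ≈ 2/√775 = 0.072. The largest footnote E shift is ln(1.008) = 0.008, about 0.11 of one SE.
- Pool share by expected patients (Appendix VI, Section 2.0): 2350 + 4400 + 2500 + 2000 + 1000 + 1500 = 13,750, and 2500/13,750 = 18.2%.
- Pooled shift under footnote E: at most 0.182 × ln(1.008) = 0.0014.
- Pooled shift under Section 11.0 ± 1 month: at most 0.182 × ln(0.986) = −0.0026 (largest in magnitude).
- The margin is ln(1.12) = 0.113, and the pooled SE at 3,390 events is 2/√3390 = 0.034.

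**5. Whether a scan could still change.** Appendix VI lists accrual as ending 6/2015, and Section 7.0 says "Initiation of treatment must begin within 14 days after randomization". Counting from 30 June 2015, 14 days plus 34 weeks is 252 days, which gives about 8 March 2016 if nobody was delayed. The latest interim analysis listed in Section 13.1 is 09/2018.

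**The case for a change.** The strongest contrary case is that the effect can be much larger than 1%. If every patient is cut off at 3 years, literal footnote E timing gives 1.035, 1.021 and 1.012 with 0%, 30% and 60% of recurrences found by symptoms. The extreme case reaches 1.067. It needs no symptomatic detection, every 6-treatment patient scanned 6 weeks after FOLFOX, and every 12-treatment patient scanned on the last permitted day. Set beside the pool's final cut-off of 1.047, that looks serious.

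The arithmetic stands, but the setting does not match the analysis. Appendix VI, Section 4.1 makes the pooled analysis event driven, with accrual spread over years and no 3-year truncation. With a common 6-year cut-off, the same model gives 1.012, 1.007 and 1.003 under footnote E, and 0.987, 0.993 and 0.997 under Section 11.0 ± 1 month. The 1.047 and 1.12 thresholds apply to the whole pool. Even a hazard ratio of 1.07 in this trial moves the pooled log hazard ratio by only 0.182 × ln(1.07) = 0.012, about a tenth of the margin.

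Two limits of the check remain. The Section 13.1 failure probabilities already refer to documented events, so using them as onset times counts detection delay twice. Actual first-scan dates are not in the documents. The Section 5.7 forms schedule lists no scan reports during celecoxib/placebo, when the first scan normally falls, and does not show whether the forms record scan dates. A table of first scans by arm may or may not be possible, and it would be descriptive only.

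**Conclusion.** The two passages word one surveillance step differently, and a careful reader will notice. The difference is clerical. The cross-reference, the shared due-date tolerance and Section 11.0's own loose upper limit for the other arm all allow footnote E to be read consistently with Section 11.0. A conflict arises only if the footnote is read literally and in isolation.

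On that reading the effect on this trial's duration hazard ratio is below 1% with staggered follow-up, and part of that range is indistinguishable from none. The alternative wording has an opposite effect that is usually no smaller, so harmonising the text brings no gain in validity. The primary celecoxib comparison is essentially unaffected, because the scan rule depends only on the duration arm and the factorial randomization balances that arm across celecoxib and placebo.

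These sizes rest on uniform first-scan timing, 0 to 30% symptomatic detection and the assumed follow-up. Which timing the sponsor intends is for the sponsor to say, and any reconciliation of the two passages would be editorial. With the first scans already past on the listed accrual dates, no scan, endpoint or result would change, and the analysis plan needs no alteration.
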